Appendix 8: EULAR Sjögren's Syndrome Patient Reported Index (ESSPRI) Score

1) How severe has your dryness been during the last 2 weeks?

No dryness		Maximal imaginable dryness									
	0	1	2	3	4	5	6	7	8	9	10

[figure not shown]
2) How severe has your fatigue been during the last 2 weeks?

[figure not shown]
No fatigue		Maximal imaginable fatigue									
	0	1	2	3	4	5	6	7	8	9	10

[figure not shown]
3) How severe has your pain (joint or muscular pains in your arms or legs) been during the last 2 weeks?

[figure not shown]
No pain		Maximal imaginable pain									
	0	1	2	3	4	5	6	7	8	9	10

[figure not shown]
Fig. 1. The EULAR Sjögren's Syndrome Patient Reported Index (ESSPRI). The ESSPRI score is the mean of the 3 scales.

Appendix 15: Algorithm for Elevated Liver Function Tests

	AST or ALT increase to				
Value Range	>=1.5x to 3xULN	>=3x to <5xULN	>=5x to <8xULN	>=3xULN with signs of liver damage ¹	>=8xULN
IP Action	Continue as planned	Reduce or interrupt IP for at least 2 weeks	Interrupt IP for at least 2 weeks	Discontinue IP ²	Discontinue IP ²
		Close observation ²	Close observation ²		
After at least 2 weeks	AST and ALT <3xULN	AST or ALT >=3xULN			
	Weekly LFTs for the first 2 weeks (biweekly for the following weeks, or more frequently at investigator's discretion)	Discontinue IP Report SAE and complete liver event page for any of abnormalities listed below ³ : - AST/ALT increase >=3xULN with signs of liver damage ¹			

¹ Signs of liver damage:

- total bilirubin >=2.0xULN OR INR >1.5, and/or
- symptoms: appearance of fatigue, nausea, vomiting, right upper abdominal quadrant pain or tenderness, fever, rash and/or eosinophilia (>5%)

² Close observation recommendations:

- Monitor 2 to 3 times per week all of the following parameters: ALT, AST, alkaline phosphatase, total bilirubin, eosinophils, INR. If local regulations allow, home visits can be performed if subjects cannot come to the clinical study center.
- Frequency of retesting can be reduced to once a week or less if abnormalities stabilize or the IP has been discontinued; however, monitoring might still be needed more frequently taking into consideration the SoC and/or changes to this.
- Based upon investigator's discretion gastroenterology or hepatology consultations, additional serology testing, imaging, and pathology assessments may be required.
- Re-query history of symptoms, prior and concurrent diseases, concomitant medication and non-prescription medicines, herbal, dietary supplements, alcohol use, recreational drug use, special diets.

- Rule out all of the following: acute viral hepatitis, autoimmune hepatitis, alcoholic hepatitis, non-alcoholic fatty hepatitis, hypoxic/ischemic hepatitis, biliary tract disease, and cholestasis.

- Re-query exposure to environmental chemical agents.

³ The following steps should be followed:

- The site should immediately contact the subject and require the subject to discontinue IP immediately. The subject should be asked to return to the site within a 48-hour window from awareness of the result.
- A full evaluation of various causes of hepatitis should be conducted (i.e. infectious, alcohol, medications, anatomical).

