- Arrhythmia or conduction abnormality, including but not limited to prolonged QTcF, where the severity is categorized as Common Terminology Criteria for Adverse Events (CTCAE) Grade 3 or higher (QTc > 500 ms and/or 60 ms over baseline on at least 2 separate ECGs 5 minutes apart) or clinically significant arrhythmia of any grade.
- Liver enzyme increase (see also [Appendix 15](#))
 - AST and/or ALT ≥ 8 times the ULN.
 - AST and/or ALT elevations ≥ 3 times ULN with signs of liver damage (i.e. with the appearance of fatigue, nausea, vomiting, right upper quadrant pain or tenderness, fever, rash and/or eosinophilia [$> 5\%$], and/or total bilirubin ≥ 2.0 times ULN or international normalized ratio [INR] > 1.5).
 - In addition, a dose interruption or reduction (if applicable) should be considered if AST and/or ALT ≥ 3 times ULN and < 5 times ULN and dosing with IP should be interrupted if AST and/or ALT ≥ 5 and < 8 times ULN.

For subjects having:

- AST or ALT ≥ 8 times ULN.
- AST or ALT ≥ 3 times ULN with signs of liver damage (i.e. with the appearance of fatigue, nausea, vomiting, right upper quadrant pain or tenderness, fever, rash, and/or

eosinophilia [>5%], and/or total bilirubin $\geq 1.5 \times \text{ULN}$ or INR > 1.5). These cases should be reported as SAEs.

the following steps will need to be performed by the investigator:

- The site should immediately contact the subject and require the subject to discontinue IP immediately. The subject should be asked to return to the site within a 48-hour window from awareness of the result.
- A full evaluation of various causes of hepatitis should be conducted (i.e. infectious, alcohol, medications, anatomical).
- An assessment of other concomitant medications and SoC should be made. The investigator should consider to whether it is in the best interest of the subject to stop/interrupt concomitant medications and SoC treatment.
- A detailed history including relevant information on alcohol use, recreational drug use, supplement consumption, any herbal remedies, family history, sexual history, travel history, history of contact with a jaundiced subject, surgery, occupational history, blood transfusion, history of liver or allergic disease, and any other potential causes attributable to a liver insult should be collected.

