11.1.4. Adverse Events of Special Interest

Not applicable.

11.1.5. Clinical Laboratory Abnormalities and Other Abnormal Assessments as Adverse Events or Serious Adverse Events

Laboratory abnormalities without clinical significance based on the investigator's judgment are not considered AEs or SAEs. However, laboratory abnormalities (e.g. clinical chemistry, hematology, and urinalysis) or other abnormal (clinical study-specific) assessments (e.g. ECG, radiography, vital signs) that require medical or surgical intervention, are associated with signs and/or symptoms, and/or lead to IP interruption, modification or discontinuation must be recorded as an AE or SAE if they meet the definition as described in Sections 11.1.1 and 11.1.2, respectively. If the laboratory abnormality is part of a syndrome, the syndrome or diagnosis is to be reported (e.g. anemia instead of decreased hemoglobin).

The following liver enzyme elevations must be reported as SAEs:

- AST or ALT $\geq 3 \times \text{ULN}$ with signs of liver damage (total bilirubin $> 2 \times \text{ULN}$ OR INR > 1.5 , and/or with the appearance of fatigue, nausea, vomiting, right upper quadrant pain or tenderness, fever, rash and/or eosinophilia [$> 5\%$]).

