#### **6.3.1.8. Presentation of Results**

The analysis will focus on AEs reported during the treatment period. AEs reported during the screening period will only be listed.

All AEs tables will show the number of subjects with TEAEs.

AEs which are not treatment-emergent will only be listed.

A summary table will be provided, showing the number (percent) of subjects with at least one:

- TEAE,
- IP-related TEAE,
- Serious TEAE,
- TEAE leading to death,
- TEAEs by worst intensity (CTCAE Toxicity Grade),
- TEAE leading to IP interruption,
- TEAE leading to IP discontinuation.

The AE terms will be presented sorted in descending order of frequency, prioritizing the GLPG3970 treatment group and then for placebo, first by system organ class, then by preferred term, and then alphabetically.

Frequency tabulations, by system organ class and preferred term, of the number (percent) of subjects with a TEAE will be presented. Similar tables will be provided by worst intensity, and for IP-related TEAEs, grade 3-4-5 TEAEs, serious TEAEs and TEAEs leading to IP discontinuation of IP.

All AE data will also be listed, including separate lists for SAEs, AEs leading to death, and AEs leading to IP discontinuation. Listings will clearly indicate AEs to be treatment-emergent or not.

In addition, AEs related to SARS-CoV-2 will be listed separately.

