### 6.3.2.8. Hepatotoxicity

Hepatotoxicity will be investigated by tabulating the aspartate aminotransferase (AST) and alanine aminotransferase (ALT) values categorized as  $>3$ ,  $>5$ ,  $>10$  and  $>20$  times their upper limit of normal (per analyte and over both analytes combined), ALP categorized as  $> 1.5$  times the upper limit and total bilirubin as  $> 2$  times the upper limit of normal. Elevations of AT (AST or ALT)  $> 3$  times their upper limits accompanied by elevated total bilirubin ( $>1.5 \times \text{ULN}$ ,  $>2 \times \text{ULN}$ ) on the same day will also be tabulated.

To assess the potential of the drug to cause severe liver damage, possible Hy's Law cases will be identified. These subjects are defined as having any elevated AT (AST or ALT) of  $>3 \times \text{ULN}$ , ALP  $<2 \times \text{ULN}$ , and associated with an increase in total bilirubin  $>2 \times \text{ULN}$  on the same day.

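### Protocol 6.4 sets two bilirubin cut-offs, 2.0 and 1.5 x ULN, for the same liver stopping condition, and Appendix 15 and Section 11.1.5 conflict with the lower one

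*Protocol*

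**What the plan says.** Four places in the protocol define the bilirubin sign that turns AST or ALT ≥3 x ULN into a liver event.

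- **Section 6.4, first liver list** (treatment must be stopped): bilirubin ≥2.0 x ULN. The list points to Appendix 15. For lesser elevations it says that "a dose interruption or reduction (if applicable) should be considered if" AST/ALT is 3 to <5 x ULN, and it requires interruption at 5 to <8 x ULN.
- **Section 6.4, second liver list**: the same AST/ALT limit, symptoms and INR limit, but bilirubin ≥1.5 x ULN. It adds: "These cases should be reported as SAEs". The first step that follows is to have the subject stop the drug at once.
- **Appendix 15, footnote 1**: "total bilirubin >=2.0xULN OR INR >1.5, and/or" symptoms or eosinophilia. Without such signs, the action at 3 to <5 x ULN is "Reduce or interrupt IP for at least 2 weeks", and at 5 to <8 x ULN it is interruption.
- **Section 11.1.5**: "The following liver enzyme elevations must be reported as SAEs", with bilirubin >2 x ULN. The same section says that abnormalities which "lead to IP interruption, modification or discontinuation must be recorded as an AE or SAE" if they meet the definition.

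SAP 6.3.1.8 has separate summary rows for serious TEAEs, "TEAE leading to IP interruption" and TEAEs leading to discontinuation. SAP 6.3.2.8 tabulates AST/ALT >3 x ULN with bilirubin >1.5 x and >2 x ULN, but only for pairs "on the same day will also be tabulated".

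**The concern.** The second list in 6.4 is a stopping rule as well as a reporting rule, so the two cut-offs compete for the same decision. No text says which one governs. The amendment log mentions no change to either value, and redaction does not explain the difference.

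Sites reading different parts of the protocol could therefore code the same laboratory picture differently: as a temporary interruption recorded as an AE, or as a permanent discontinuation with an SAE. SAP 1 states that the Safety Monitoring Committee recommended termination because of a liver toxicity signal. TEAEs are one of the two primary endpoints, and only the primary endpoint and safety analyses remain. A reader of the abbreviated CSR will look at exactly these rows and cannot tell which rule produced the counts.

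**Working it through.** There is no plan figure to reproduce. The check compares the four texts on one type of subject: no listed symptom, INR ≤1.5, eosinophils ≤5%.

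**Step 1. Vary bilirubin, with AST/ALT at 3.5 x ULN.** The stopping texts are 6.4 first list (≥2.0), 6.4 second list (≥1.5) and Appendix 15 (≥2.0). For SAE reporting I compare only 6.4 second list (≥1.5) and 11.1.5 (>2). Appendix 15 is left out of the SAE count because the available text does not preserve the table layout, so it is unclear at what stage its SAE instruction applies.

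| Bilirubin, x ULN | Texts requiring a stop (of 3) | Texts requiring an SAE (of 2) |
|---|---|---|
| 1.4 | 0 | 0 |
| 1.5 | 1 | 1 |
| 1.7 | 1 | 1 |
| 1.99 | 1 | 1 |
| 2.0 | 3 | 1 |
| 2.1 | 3 | 2 |

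The texts disagree from 1.5 to <2.0 x ULN. At exactly 2.0 x ULN only the SAE rules disagree, because 11.1.5 uses a strict inequality. The 1.5 value is the outlier among the four.

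**Step 2. Vary AST/ALT, with bilirubin at 1.7 x ULN.**

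| AST/ALT, x ULN | 6.4 first list | 6.4 second list | Appendix 15 |
|---|---|---|---|
| 3 to <5 | consider interruption or reduction | stop, SAE | reduce or interrupt |
| 5 to <8 | interrupt | stop, SAE | interrupt |
| ≥8 | stop | stop | stop |

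The stopping conflict is thus confined to AST/ALT below 8 x ULN. At exactly 3.0 x ULN there is a further small overlap: Appendix 15's continue-as-planned column runs up to and includes 3 x ULN, while its next column starts there.

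**Step 3. Effect of one reclassified subject on a table row.** Planned sizes are 20 active and 10 placebo (Protocol 9.1).

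- Active: 1/20 = 5 percentage points.
- Placebo: 1/10 = 10 percentage points.
- The number actually treated is not given. If it were 10 active subjects (an assumption), the shift would be 1/10 = 10 points.

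**The case against.** **The study is over.** The liver signal was found under this wording, and new wording cannot change any dosing. This stands and is the main reason for a minor rating.

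**The two lists in 6.4 can be read as cumulative.** Meeting the second list requires a stop, and the first list's softer instruction does not forbid one. Section 6.4 also lets the investigator stop for safety concerns, and Appendix 15 keeps such subjects under close observation. Appendix 15 also appears to require stopping if AST or ALT is still ≥3 x ULN after the pause. This narrows the conflict inside 6.4. It does not remove the clash with Appendix 15, to which 6.4 sends the reader, or with the SAE rule in 11.1.5.

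**The lower value may be a deliberately cautious reporting threshold.** This fails. The second list also demands immediate discontinuation, and the section devoted to mandatory liver SAEs sets its limit at 2 x ULN.

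**The SAP already shows both bilirubin bands.** A reader might infer that the >1.5 x count minus the >2 x count caps the number of subjects affected. It does not:

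- The protocol rules carry no same-day limit, while the SAP rows do.
- A subject at 1.7 x ULN who later exceeds 2 x ULN, with AST/ALT still >3 x ULN both times, enters both rows and cancels (1 − 1 = 0), although the instructions conflicted at the earlier draw.
- SAP 6.3.2.1 restricts tables to central-laboratory results; local results are only listed.

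**Conclusion.** The contradiction is certain on the text and wrong as written. Its importance is minor. It applies only to the band set out above, and the documents do not say how many subjects, if any, fell in it. The 5- and 10-point shifts describe one hypothetical subject against planned group sizes and are not estimates of error in the results.

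Two stronger readings are not supported. A reader might infer that the mixed wording contributed to liver injury or delayed the stop; the documents contain no subject-level data on which to say so. A reader might also infer that the SAP's same-day rule is an error that conceals possible Hy's Law cases. It is true that a subject whose AST and ALT have both fallen to 3 x ULN or below before bilirubin exceeds 2 x ULN drops out of the combined rows. That subject still appears in the single-analyte rows, profile plots and flagged listings, so a sequential row would be a supplement and not a correction.

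**What to change.** **One cut-off in all four places.** Choosing ≥2.0 x ULN needs two edits: the second list in 6.4, and the inequality sign in 11.1.5. Choosing ≥1.5 x ULN, if the sponsor prefers the more cautious rule, needs three: the first list in 6.4, Appendix 15 footnote 1, and 11.1.5. With the study terminated, this matters mainly for the record and for any protocol that reuses the text.

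**In the CSR.** List every subject with AST/ALT ≥3 x ULN and bilirubin 1.5 to <2.0 x ULN, using central and local results and not limited to same-day pairs. Show the drug action taken and the SAE status for each. Add one sentence stating which bilirubin rule was applied to SAE reporting and discontinuation. The cost is one short listing and one sentence.

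**Optional.** Add a supplementary row, labelled post hoc, for bilirubin >2 x ULN on or after AST/ALT >3 x ULN within a stated interval, and keep the same-day rows. The interval would be a choice made after the liver signal was known. The spacing of scheduled visits is a weak basis for it, because Appendix 15 asks for testing 2 to 3 times a week in subjects under close observation, reducible to weekly or less. The cost is one row, and possibly one or two extra cases to review clinically.

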## VERSION HISTORY

SAP Amendment #	Date	Description of changes
SAP Version Final 1.0	17-Dec-2021	N/A

## LIST OF ABBREVIATIONS

AE	adverse event
ALT	alanine aminotransferase
AST	aspartate aminotransferase
ATC	anatomical therapeutic chemical
AUC	area under the plasma concentration-time curve
BLOQ	below lower limit of quantification
BMI	body mass index
C3	complement component 3
C4	complement component 4
CI	confidence interval
CL	clearance
CLCr	creatinine clearance
CRF	case report form
CRO	contract research organization
CRP	C-reactive protein
CSP	clinical study protocol
CSR	clinical study report
CTCAE	Common Terminology Criteria for Adverse Events
C tau	trough concentration
CTX	serum C terminal telopeptide type I collagen
ECG	electrocardiogram
eCRF	electronic case report form
ED	early discontinuation
eGFR	estimated glomerular filtration rate
ESSDAI	EULAR Sjögren's Syndrome Disease Activity Index
ESSPRI	EULAR Sjögren's Syndrome Patient Reported Index
EULAR	European League against Rheumatism
FAS	full analysis set
FU	follow-up
GLSM	geometric LS-mean
GM	geometric mean
GSD	geometric standard deviation
GSE	geometric standard error
H	high, above the upper limit of the normal range

HDL	high-density lipoprotein
High	high specificity test
HOMA-IR	homeostatic model assessment of insulin resistance
HR	heart rate
ICF	informed consent form
ICH	International Council for Harmonization of Technical Requirements for Pharmaceuticals for Human Use
IP	investigational product
INF	infinity
IWRS	interactive web response system
L	low, below the lower limit of the normal range
LDL	low-density lipoprotein
LLN	lower limit of the normal range
LLOQ	lower limit of quantification
LRV	lower reference value
LS	least squares
LSM	least square mean
MedDRA	medical dictionary for regulatory activities
██████████	
MMRM	mixed models for repeated measures
n	number of non-missing data points
N	normal, with the limits of the normal range
NCI CTCAE	National Cancer Institute Common Terminology Criteria for Adverse Events
NRI	non-responder imputation
OC	observed cases
██████████	
PK	pharmacokinetic(s)
pop-PK	population PK
PR	pulse rate
pSS	primary Sjögren's Syndrome
██████████	
QTc	corrected QT interval
QTcF	QT interval corrected for the heart rate using Fridericia's formula
RR	respiratory rate
SAE	serious adverse event

SAP	statistical analysis plan
SD	standard deviation
SDTM	study data tabulation model
SE	standard error
[REDACTED]	[REDACTED]
SI	standard international
[REDACTED]	[REDACTED]
SMC	Safety Monitoring Committee
SoC	standard-of-care
TE	Treatment-emergent
TEAE	treatment-emergent adverse event
[REDACTED]	[REDACTED]
TLF	tables, listings and figures
TV	target value
ULN	upper limit of the normal range
ULOQ	upper limit of quantification
[REDACTED]	[REDACTED]
WHO	World Health Organization

## 1. INTRODUCTION

This statistical analysis plan (SAP) describes the final statistical analyses of study GLPG3970-CL-207. The results of the analysis will be described in the clinical study report (CSR).

Technical details on derivations and mock tables, listings and figures (TLFs) will be presented in a separate document.

The statistical analysis will process and present the results following the International Council for Harmonization (ICH) standards, particularly the ICH-E3, ICH-E6, ICH-E9, ICH-R9 (R1) and ICH-E14 guidelines.

On 26 November 2021, the Safety Monitoring Committee recommended to immediately terminate Study GLPG3970-CL-207 due to a safety signal of liver toxicity. Therefore, the GLPG3970-CL-207 study was prematurely stopped. In view of this, only the primary endpoint and safety analyses will be performed. Results will be presented in an abbreviated CSR. Any provisions no longer applicable following premature study termination are highlighted in grey.

## 2. STUDY DESIGN AND OBJECTIVES

### 2.1. Study Objectives

#### 2.1.1. Primary Objectives

- To evaluate the efficacy of GLPG3970 compared to placebo on the signs and symptoms of primary Sjögren's Syndrome (pSS).
- To evaluate the safety and tolerability of GLPG3970 compared to placebo.

#### 2.1.2. Secondary Objectives

- To further characterize the efficacy of GLPG3970 compared to placebo on the patient-reported signs and symptoms of pSS.
- To characterize the pharmacokinetics (PK) of GLPG3970.

#### 2.1.3. Other Objectives

## 2.2. Study Endpoints

[figure not shown]
### 2.2.1. Primary Endpoints

- Change from baseline in European League against Rheumatism (EULAR) Sjögren's Syndrome Disease Activity Index (ESSDAI) score at Week 12.
- Number, incidence, and severity of treatment-emergent adverse events (TEAEs).

### 2.2.2. Secondary Endpoints

- Change from baseline in EULAR Sjögren's Syndrome Patient Reported Index (ESSPRI) score at Week 4, 8, and 12.
- Change from baseline in ESSDAI score over time at Week 4, 8, and 12.
- Observed GLPG3970 plasma trough concentration ( $C_{\text{tau}}$ ).

### 2.2.3. Other Endpoints

## 2.3. Study Design

This is a Phase 2a, randomized, double-blind, placebo-controlled, parallel-group, multicenter study to evaluate the efficacy, safety, tolerability, PK, [REDACTED] of orally administered GLPG3970 for 12 weeks in adult subjects with active pSS.

One dose level of GLPG3970 will be evaluated in 30 subjects who will be randomized 2:1 to receive GLPG3970 (400 mg [2 x 200 mg] qd) or matching placebo, respectively.

The study will consist of 3 study periods:

[figure not shown]
- Screening period: up to 4 weeks with 1 study visit. During the Screening visit, subjects will be selected based on the eligibility criteria. Subjects already on treatment will remain on a stable standard of care (SoC) treatment during the study.
- Treatment period: 12 weeks with up to 5 study visits (Days 1, 8, 29, 57, and 85). At any time during the course of the study, phone calls or unscheduled visits can be added if deemed necessary by the investigator. Subjects will receive GLPG3970 or placebo qd.
- Follow-up (FU) period: 4 weeks with 1 study visit. Subjects remain on stable SoC treatment, if applicable.

The subjects will be in the study for a duration of 20 weeks: up to 4 weeks of screening, 12 weeks of treatment, and 4 weeks of FU.

Refer to the Schedule of Assessments ([Section 2.5](#)) for further details.

A schematic diagram of clinical study design and periods is provided in [Figure 1](#).

**Figure 1 Schematic Diagram**

## 2.4. Clinical Study Protocol (CSP) and CSP Amendments

This SAP was based on the protocol version 7.0, dated 12-May-2021.

## 2.5. Scheduled of Assessments

The study assessments will be undertaken at time points as specified in the Schedule of Assessments ([Table 1](#)). For detailed instructions on the clinical study procedures, please see the relevant CSP sections and CSP Section 8.1, “Timing of Assessments”.

**Table 1 Schedule of Assessments**

EVENT	SCREENING PERIOD	TREATMENT PERIOD 						FOLLOW-UP PERIOD
		1	2	3	4	5	ED 	
Study Visit	S	1	2	3	4	5	ED 	Follow-up Visit
Study Week	-4 to -1	Baseline	1	4	8	12		
Study Day (D) ± Days	-28 to -1	1	8±1	29±2	57±2	85±2	Early treatment discontinuation	28 ± 3 after last IP dosing
Informed consent	✓							
Inclusion/exclusion criteria	✓	✓						
Demographics	✓							
Medical history	✓							
Physical examination	✓	✓	✓	✓	✓	✓	✓	✓
Vital signs	✓	✓	✓	✓	✓	✓	✓	✓
Body weight and height 	✓	✓	✓	✓	✓	✓	✓	✓
12-lead ECG 	✓	Predose, 1.5h, 3h, 4.5h postdose 	Predose	Predose	Predose	Predose	✓	✓

 On dosing days, all assessments are to be performed predose, unless otherwise specified. Subjects who discontinue treatment early will be requested to return for an ED visit and to return for a FU visit 28 ± 3 days after last IP administration. Height only to be measured at screening. At Visit 1 (Day 1), triplicate ECGs will be recorded predose and at 4.5 hours postdose. At all other timepoints, single ECGs will be taken.

EVENT	SCREENING PERIOD	TREATMENT PERIOD 						FOLLOW-UP PERIOD
		1	2	3	4	5	ED 	
Study Visit	S	1						Follow-up Visit
Study Week	-4 to -1	Baseline	1	4	8	12		
Study Day (D) ± Days	-28 to -1	1	8±1	29±2	57±2	85±2	Early treatment discontinuation	28 ± 3 after last IP dosing
QuantiFERON-TB Gold test	✓							
SARS-CoV-2 RT-PCR test 	✓	✓					As needed	
SARS-CoV-2 serology test 		✓					As needed	
Randomization		✓						
Blood collection								
– Safety (hematology, coagulation, chemistry)	✓	✓ 	✓	✓	✓ 	✓ 	✓	✓
– Safety (HBV, HCV, HIV serology)	✓							
– Pregnancy test serum (all females)	✓							
– FSH test (WOnonCBP, non-surgical postmenopausal women)	✓							

 RT-PCR from a nasal swab sample at screening and RT-PCR from a nasal swab sample and serology testing at Visit 1 (Day 1), and as needed when subject presents signs and symptoms of SARS-CoV-2 infection.

 SARS-CoV-2 RT-PCR and serology tests can (optionally) be sampled by a nurse at the subject's home 2-3 days before Visit 1 (Day 1).

 Fasted glucose, fasted insulin, and HOMA-IR only at Visit 1, 4, and 5.

EVENT	SCREENING PERIOD	TREATMENT PERIOD 						FOLLOW-UP PERIOD
		1	2	3	4	5	ED 	
Study Visit	S	1						Follow-up Visit
Study Week	-4 to -1	Baseline	1	4	8	12		
Study Day (D) ± Days	-28 to -1	1	8±1	29±2	57±2	85±2	Early treatment discontinuation	28 ± 3 after last IP dosing
– Blood samples for PK GLPG3970		Predose  , 0.5-1.5h, 2-2.5h, 4.5h  postdose 	Predose 	Predose 	Predose  , 0.5-1.5h, 2-2.5h postdose 	Predose 	✓	
–								
–								
Urine sample								
– Safety (urine)	✓	Predose	Predose	Predose	Predose	Predose	✓	✓

 At Visit 1, 2, 3, 4, and 5, PK sample to be taken within 30 minutes predose.

 At Visit 1, the PK sample collected at 4.5 hours postdose must be taken immediately after the triplicate ECG.

 At Visit 1, 4, and 5 subjects must come for the study visits in a fasting state (no food intake for at least 8 hours). If the postdose samples could not be collected at Visit 4, they should be collected at Visit 5. It is important that the PK samples are collected on the same day.

EVENT	SCREENING PERIOD	TREATMENT PERIOD 						FOLLOW-UP PERIOD
		1	2	3	4	5	ED 	
Study Visit	S	1						Follow-up Visit
Study Week	-4 to -1	Baseline	1	4	8	12		
Study Day (D) ± Days	-28 to -1	1	8±1	29±2	57±2	85±2	Early treatment discontinuation	28 ± 3 after last IP dosing
- Pregnancy testing (UPT, dipstick) (WOCBP only)		Predose	Predose	Predose	Predose	Predose		
Subject diary evaluation		✓	✓	✓	✓	✓	✓	✓
ESSDAI	✓	✓		✓	✓	✓	✓	
ESSPRI	✓	✓		✓	✓	✓	✓	

EVENT	SCREENING PERIOD	TREATMENT PERIOD 						FOLLOW-UP PERIOD
		1	2	3	4	5	ED 	
Study Visit	S	1	2	3	4	5	ED 	Follow-up Visit
Study Week	-4 to -1	Baseline	1	4	8	12		
Study Day (D) ± Days	-28 to -1	1	8±1	29±2	57±2	85±2	Early treatment discontinuation	28 ± 3 after last IP dosing
Dispense IP		✓	✓	✓	✓			
IP administration 		Once daily throughout the treatment period						
AE and concomitant medication		throughout the study						

[figure not shown]
 At Visit 1 (Day 1), the IP will be administered at the study site in a fasted state. Breakfast will be provided to the subject 0.5-1 hour after the IP intake. Lunch should be eaten 1 hour before or after the ECG measurement at 4.5 hours postdose. At all other dosing days (including Visit 2, 3, 4, and 5), the IP should be taken in a fed state (together with a meal).

